1.1. Institutions involved and responsible persons

| | |
|------------------------------------|--|
| Scientific Directors | [name] Medizinische Klinik und Poliklinik II Rheumatologie/Klinische Immunologie [name] Medizinische Klinik und Poliklinik II. Rheumatologie/Klinische Immunologie [name] Klinik und Poliklinik für Nuklearmedizin [name] Klinik und Poliklinik für Nuklearmedizin |
| Participating clinics/institutions | Medizinische Klinik und Poliklinik II Rheumatologie/Klinische Immunologie Direktor der Klinik: [name]. [name] Schwerpunktleiter: [name]. [name] Klinik und Poliklinik für Nuklearmedizin Direktor der Klinik: [name]. med. [name] Institut für diagnostische und interventionelle Radiologie Direktor des Instituts: [name]. med. [name] |

2. Synopse

| | |
|-------------------------|--|
| TITLE | CXCR4 PET/CT for detecting inflammatory activity in systemic sclerosis |
| DATE VERSION | 09.FEB. 2022 Version 4 |
| AIMS | As pilot study, visualization of inflammatory activity in systemic sclerosis using CXCR4-PET/CT. |
| RATIONALE FOR THE STUDY | Systemic sclerosis (SSc) is a heterogeneous disease characterized by inflammatory, vasculopathic, and fibrotic changes. Initially, inflammatory changes usually occur, which progress to fibrosis. Various organ systems such as the lungs, skin, heart, and gastrointestinal tract are affected. Early detection of inflammatory activity is therefore important in order to prevent consequential damage, in particular irreversible fibrosis. Since the inflammatory foci can spread throughout the entire body, there is a need to be able to detect inflammatory activity over a large area. The 68Ga-Pentixafor-based imaging of the CXCR4 chemokine receptor, which is expressed on immune system cells such as lymphocytes and macrophages, offers a useful approach here, as it allows specific inflammatory cells to be visualized that migrate to inflammatory lesions via the corresponding ligand (CXCL12) and are involved in the pathogenesis of SSc. To date, only chest CT has been used to diagnose and monitor the progression of pulmonary fibrosis in SSc. This non-functional imaging technique makes it virtually impossible to assess inflammatory activity. |
| NUMBER OF PARTICIPANTS | 12 patients (pilotstudy) |
| STUDY POPULATION | Patients with SSc, with a disease duration of less than 5 years and with interstitial lung disease (ILD) |
| STUDY DESIGN | Explorative, prospective pilotstudy, not blinded, not randomized |
| PRIMARY ENDPOINT | Measurement of the maximum measurable 68Ga-pentixafor tracer activity in CXCR4-PET/CT |
| DURATION | Ca. 1 year |
| NUMBER OF CENTERS | Monocentric at the University Hospital Würzburg |

3. Background

Interstitial lung disease (ILD) is the most common cause of death in patients with systemic sclerosis (SSc). With regard to the pathogenesis of ILD, but also of other manifestations of SSc, it is postulated that leukocytes initially migrate into the tissue and cause an inflammatory reaction, which subsequently leads to fibrosis. Active inflammation can be treated much more effectively with medication than fibrosis.

The distinction between fibrosis that has already occurred, i.e., is usually irreversible, and the active stage with inflammation is therefore of great therapeutic importance.

Stromal cell-derived factor 1 (SDF-1 or synonymously CXCL12) and its receptor C-X-C motif chemokine receptor 4 (CXCR4) are involved in angiogenesis and the mediation of leukocyte migration, which is an important pathomechanism in SSc. Consistent with this, high SDF-1 and CXCR4 expression is found in the skin of SSc patients, especially in the early stages of the disease, which decreases with increasing disease duration (Cipriani et al. 2006).

SSc patients may have antibodies against CXCR4. Higher antibody titers are associated with more severe lung involvement and poorer lung function. CXCR4-positive mononuclear cells from peripheral blood are found to be reduced in SSc (Weigold et al. 2018).

The consideration of the CXCR4/CXCL12 axis in SSc therefore appears promising.

The Clinic and Polyclinic for Nuclear Medicine at Würzburg University Hospital has a manufacturing license (issued by the Regional Council of Upper Franconia) for the production of 68Ga-Pentixafor for imaging the chemokine receptor CXCR4. CXCR4 is expressed by many cells of the hematopoietic system, such as stem cells, neutrophil granulocytes, monocytes, T lymphocytes, B lymphocytes, pre-B cells, dendritic cells, and macrophages. It is also detectable on most malignant cells.

During inflammatory processes, CXCL12, the ligand of CXCR4, is upregulated in the affected tissue. The chemotactic effect of this ligand leads to the migration of CXCR4-positive cells into the inflamed area, which can be visualized in PET using the CXCR4-specific tracer 68Ga-Pentixafor. A significant advantage over the previous standard tracer F-18 deoxyglucose is its independence from glucose metabolism.

Based on experience gained in the use of CXCR4-PET/CT in malignant diseases in studies conducted at the University Hospital of Würzburg, it can be assumed that this new tracer should enable sensitive visualization of inflammatory processes in SSc and thus functional imaging. This assumption is supported by the fact that CXCR4 can be visualized using PET/CT in idiopathic pulmonary fibrosis (IPF) – a clinical picture that is very similar to ILD in SSc in terms of clinical presentation, prognosis, and treatment (Derlin et al. 2021).

To date, only non-functional cross-sectional imaging using chest CT, which is routinely performed every 1-2 years, has been established for the diagnosis and monitoring of pulmonary fibrosis in SSc.

4. Aims of the study

Testing the hypothesis that tracer activity in ⁶⁸Ga-pentixafor PET/CT correlates with disease activity in the lungs (heart, and skin) and that activity is associated with disease progression, i.e., worsening fibrosis in the corresponding organ.

Another objective of the study is to characterize CXCR4 expression in monocytes, granulocytes, and lymphocytes in peripheral blood using flow cytometry and, if necessary, cell culture analysis, as well as to measure CXCL12 and CXCR4 antibodies in peripheral blood. The leukocyte populations mentioned above are particularly important for the pathogenesis of inflammatory changes in SSc. A correlation with ⁶⁸Ga-pentixafor uptake will be investigated.

A further objective is to correlate ⁶⁸Ga-pentixafor uptake with routinely available clinical, imaging, and laboratory parameters.

The aim is to use the data collected to perform a well-founded case number calculation for a subsequent prospective study.

5. Study design and endpoints

5.1. Design

The project is designed as a monocentric, exploratory, and prospective pilot study that is neither blinded nor randomized. The pilot study will take approximately one year to complete. For individual participating patients, participation in the study ends with the planned CXCR4 PET/CT examination. The parameters routinely collected after 6 and 12 months will be included in the evaluation.

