5.2. Endpoints

The primary endpoint of the pilot series is to determine the maximum measurable ⁶⁸Ga-Pentixafor uptake in CXCR4-PET/CT in the area of fibrotic pulmonary changes.

Secondary endpoints:

- Determination of the maximum measurable ⁶⁸Ga-Pentixafor uptake in CXCR4-PET/CT in the heart
- Correlation of the measured tracer activity with clinical, laboratory, and imaging findings.

The secondary endpoints serve to classify the measured tracer activities should significant fluctuations occur within the group.

6. Course of the study

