All CT and PET examinations are initially evaluated visually to determine the intensity and extent of the inflammatory processes. For semi-quantitative assessment of regional inflammatory activity, regions of interest (ROI) are placed in areas of increased [^{68}Ga]-pentixafor uptake using TrueD software (Siemens Medical Solutions, Knoxville, TN). The SUV(mean/max/peak) is calculated within the ROI according to the formula:

SUV = specific activity concentration (Bq/g) x body weight (in g) / injected activity (Bq). In addition to the SUV, other standard quantification parameters, such as the CXCR4-positive volume or mathematically extracted items (e.g., radiomics parameters, Interview Fusion, Mediso Medical Imaging, Hungary), are determined. In [68Ga]-pentixafor PET/CT, the SUVs are correlated with tracer uptake in the background (e.g., in the liver) and a ratio is formed.

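### Regions of interest are placed by eye with no rule keeping the reader unaware of the baseline clinical data, so the exploratory uptake-activity correlations could be inflated; locking the SUV values first would prevent this

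*Protocol*

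**What the plan says.** - **Blinding.** Section 5.1 describes a single-centre exploratory pilot that is "neither blinded nor randomized". The synopsis agrees: "Explorative, prospective pilotstudy, not blinded, not randomized".
- **Order of events.** Section 6.3 places the baseline parameters at step d and the PET/CT at step e. The parameters include the modified Rodnan skin score, cardiac markers, lung function, extent of lung involvement and the EUSTAR activity index.
- **Image reading.** Section 6.4 (Image evaluation) states: "All CT and PET examinations are initially evaluated visually to determine the intensity and extent of the inflammatory processes". For the semi-quantitative step, "regions of interest (ROI) are placed in areas of increased" uptake, and "The SUV(mean/max/peak) is calculated within the ROI according to the formula" that follows. CXCR4-positive volume and radiomics parameters are also derived. The section gives no uptake threshold, no anatomical placement rule and no limit on what the reader may know.
- **Use of the values.** Section 4 sets out the hypothesis that uptake correlates with disease activity and is associated with later worsening of fibrosis. Section 5.2 lists as a secondary endpoint: "Correlation of the measured tracer activity with clinical, laboratory, and imaging findings". Section 4 also intends the data to support a sample-size calculation for a subsequent study.
- **Primary endpoint and question.** Section 5.2 defines the endpoint as the "maximum measurable ⁶⁸Ga-Pentixafor uptake in CXCR4-PET/CT in the area of fibrotic pulmonary changes". Section 8.2 words the primary question as maximum uptake in the ILD area against normal lung.

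**The concern.** The study has no treatment arms, so there is no treatment to blind. That does not explain why the image reader should be free to know the patient's clinical status. The reader decides by eye how extensive the uptake is and where to draw the regions, and the result is correlated with data that may already be in the file. If the reader looks harder, or draws more generously, in patients known to be more severely affected, part of the correlation comes from the reader. A larger sample would estimate the inflated correlation more precisely without removing the inflation.

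The exposed results are the section 4 hypothesis and the section 5.2 correlations. They are exploratory, but they are to feed the planning of the next study, and an inflated correlation would make that study too small.

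There is a second route in the other direction. Section 4 relates uptake to progression, the 12-month chest CT contributes to judging progression, and nothing says that whoever assesses that CT is unaware of the PET result.

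**Working it through.** **1. The plan's own figure.** The appendix takes r = -0.75, two-sided alpha 0.05, power 0.80 and a Pearson correlation, and arrives at 11 patients. Simulating the Pearson test under bivariate normality (200,000 replicates) gives power 0.779 at n = 10 and 0.826 at n = 11, so 11 is reproduced. The 12 enrolled allow for 10% dropout (11 × 1.10 = 12.1; 11/0.90 = 12.2). Masked reading changes neither figure.

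**2. The pathway, from the text.** Clinical indices are collected (6.3, step d); the scan follows (6.3, step e); regions are chosen by eye (6.4); uptake is correlated with the indices (4 and 5.2). Every link is in the protocol except one: whether the reader actually sees the indices is not stated either way.

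**3. Effect on a correlation (illustration).** Let X be uptake as an uninfluenced reader would measure it and Z clinical severity, both in SD units, with true correlation ρ. Suppose a reader who knows Z records X' = X + kZ. Then

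corr(X', Z) = (ρ + k) / √(1 + 2kρ + k²).

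The value of k is an assumption; no figure in the documents informs it.

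| k (assumed) | true ρ = 0 appears as | true ρ = 0.50 appears as |
|---|---|---|
| 0 | 0 | 0.50 |
| 0.1 | 0.10 | 0.57 |
| 0.2 | 0.20 | 0.63 |
| 0.3 | 0.29 | 0.68 |

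For k = 0.2 and ρ = 0.50: 0.70/√1.24 = 0.629. For k = 0.3 and ρ = 0.50: 0.80/√1.39 = 0.679.

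**4. Chance of a false signal at n = 12.** With ρ = 0 the induced correlation is k/√(1 + k²). The simulated probability of a two-sided result below 0.05 is:

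| k (assumed) | Pearson | Kendall |
|---|---|---|
| 0 | 0.05 | 0.05 |
| 0.1 | 0.06 | 0.06 |
| 0.25 | 0.12 | 0.10 |
| 0.5 | 0.32 | 0.24 |
| 1.0 | 0.79 | 0.67 |

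Both tests are shown because the appendix plans with Pearson and section 8.2 names Kendall's tau for the primary question. Reading without knowledge of Z corresponds to the first row.

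**5. Effect on the next study.** Using n = ((1.960 + 0.842)/atanh r)² + 3, rounded up, and power = Φ(√(n − 3) × atanh 0.50 − 1.960):

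| Planned on r | n | power if ρ = 0.50 |
|---|---|---|
| 0.50 (k = 0) | 29.01, so 30 | 81% |
| 0.57 (k = 0.1) | 22 | 67% |
| 0.63 (k = 0.2) | 18 | 57% |
| 0.68 (k = 0.3) | 15 | 48% |

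**6. Which measures are exposed.** SUVmax is the hottest value in a region, so drawing the region differently changes it only if the hottest spot is brought in or left out. SUVmean, CXCR4-positive volume and the visual rating of extent depend directly on what is drawn or judged. A small k is therefore more plausible for SUVmax than for these.

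**The case against.** The strongest reply has five parts.

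- **Reader knowledge is not documented.** The label in section 5.1 describes the study as a whole. The protocol does not say who reads the images, when, or with what information. A reader might infer that the images are in fact read with the clinical file open; the documents do not support that, only that nothing prevents it. Moreover, section 6.5 draws the blood for leukocyte profile, CXCL12 and CXCR4 antibodies through the cannula placed for the tracer, so those results do not exist before the scan day. This stands.
- **The main measure is fairly robust.** The primary endpoint is a maximum in fibrotic lung, and k for a maximum may be close to zero. This stands for SUVmax, less so for the other quantities in section 6.4.
- **The primary question is different.** Section 8.2 compares ILD area with normal lung within one scan. A reader might infer that masking would protect this too. It would not: a reader unaware of the clinical data would still place regions where uptake looks high. That needs a placement rule based on CT or otherwise fixed in advance.
- **The correlations are exploratory,** in a pilot of 12 patients. True, but section 4 intends to plan the next study from these data.
- **Masking is not free.** Separate departments do not guarantee separate information, and the documents say nothing about reading staff. The 12-month CT follows routine practice, so a masked assessment might require a second read. This stands, and limits what can be asked for the CT.

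**Conclusion.** The point holds as a modest, inexpensive improvement. The protocol declares an open study, has regions placed by eye after the clinical indices are collected, and correlates the results with those indices. Expectation bias in the section 4 and section 5.2 correlations is therefore possible, and nothing in the protocol prevents it.

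Its size cannot be derived from the documents. Under the assumed range k = 0 to 0.3, a true 0.50 appears as 0.50 to 0.68, and a follow-up study planned on that figure would have about 81% down to 48% power. This assumes a linear shift in the direction of the study hypothesis; if readers do not see the data, or do not act on them, the effect is nil. A reader might infer that reader expectation could by itself create the correlation. That needs the large assumed shifts in the table (0.5 to 1 SD per SD), for which there is no evidence here; inflation is the fair description. The primary within-scan comparison is outside this point.

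**What to change.** Add a short paragraph to section 6.4 (Image evaluation) stating that:

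- the nuclear medicine reader places the regions and locks the SUV values (and the volume and visual ratings) under the patient code before seeing the baseline clinical, lung-function or laboratory values;
- where the routine workflow allows it without an additional read, the 12-month CT is assessed without knowledge of the PET values. Where it does not, the report should say that the CT was assessed with the PET result available.

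Section 5.1 can still describe the study as open, with a cross-reference to this paragraph.

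The cost is a locking step and request forms worded neutrally. The patient number and pseudonymised data file already exist under section 9. Sample size, visits and scan procedure are unchanged.

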5.2. Endpoints

The primary endpoint of the pilot series is to determine the maximum measurable ⁶⁸Ga-Pentixafor uptake in CXCR4-PET/CT in the area of fibrotic pulmonary changes.

Secondary endpoints:

- Determination of the maximum measurable ⁶⁸Ga-Pentixafor uptake in CXCR4-PET/CT in the heart
- Correlation of the measured tracer activity with clinical, laboratory, and imaging findings.

The secondary endpoints serve to classify the measured tracer activities should significant fluctuations occur within the group.

6. Course of the study

6.1. Inclusion criteria

- Confirmed diagnosis of SSc based on the 2013 ACR/EULAR criteria
- Disease duration less than 5 years (onset of the first non-Raynaud's symptom within the last 5 years)

- Evidence of ILD in computed tomography
- Patient's ability to understand the information provided
- Patient of legal age
- Exclusion of contraindications for performing a PET/CT examination (see below)

Patients are informed in detail, both in writing and verbally, about the purpose of the examination and the risks of participating in the pilot study. The information is provided with sufficient time for consideration before the planned PET/CT scan. The Declaration of Helsinki and the guidelines of Good Clinical Practice are observed in all respects. Consent to participate in the pilot study and any questions/special circumstances are documented in writing by the patient's signature on the consent form, which must also be signed by the physician providing the information.

6.2. Exclusion criteria

- Following autologous stem cell transplantation
- Presence of pulmonary hypertension
- Contraindications for performing a PET/CT scan
- Pregnancy
- Breastfeeding
- Allergies to 68Ga-Pentixafor
- Patient's inability to understand and give informed consent

6.3. Recruitment and study procedure

Timeline of the pilot study:

- a. Screening of patients during their appointment at the rheumatology outpatient clinic
- b. Review of inclusion and exclusion criteria
- c. Inclusion in the pilot study
- d. Determination of baseline parameters:
 - i. mRSS
 - ii. Troponin/NT-pro-BNP
 - iii. Leukocyte differentiation (flow cytometry/cell culture), CXCL12 determination, and CXCR4 antibody determination
 - iv. Echocardiography
 - v. Lung function with 6-minute walk test
 - vi. Collection of indices for probability of progression (analogous to the INBUILD study, Flaherty et al. 2019), extent of lung involvement (according to Goh et al. 2008) and activity index according to EUSTAR (Valentini et al. 2017).
 - vii. ANA/ENA, fibrillarin, RNA polymerase III, myositis line blot
- e. Performance of a CXCR4 PET/CT scan
- f. Routine clinical check-ups are performed after 6 and 12 months, including points i.-vi.
- Follow-up checks of ILD using chest CT are performed after 12 months, in accordance with routine clinical practice.

6.4. PET/CT scanning

The PET/CT examination is performed in accordance with the current guidelines of the German Society of Nuclear Medicine and the European Association of Nuclear Medicine. Patients are informed about the planned examination by the responsible study physician and give their written consent to the examination. The explanatory discussion takes place with sufficient time for consideration before the start of the examination.

Patient preparation

Patients do not need to fast before imaging with the tracer ^{68}Ga -Pentixafor. A venous cannula is inserted to administer the tracer. Before the start of image acquisition, patients should empty their bladder completely so that they do not become restless during the examination due to a possible urge to urinate.

After the examination, patients should drink plenty of fluids and empty their bladder frequently to support the renal excretion of ^{68}Ga -Pentixafor and thus minimize radiation exposure.

Image acquisition

The clinical examinations are performed using a PET/CT hybrid scanner (Siemens mCT, Knoxville, TN). The dose coefficient for ^{68}Ga -Pentixafor is $1.56 \cdot 10^{-2}$ mSv/MBq. The radiation exposure for a PET examination with an application of 100-130 MBq is therefore 2.3 mSv. In comparison, the radiation dose for an adult human from natural and civilizational radiation exposure is approximately 2.1 mSv per year; This means that the examination corresponds approximately to the dose of natural radiation received by an adult in Germany (Federal Office for Radiation Protection, accessed on February 9, 2022).

Image acquisition for ^{68}Ga pentixafor PET takes place 45 minutes after injection. The measurement range extends from the neck to the pelvis. In 3D mode, measurements are taken for 2 minutes per bed position, and image reconstruction is performed using an OSEM algorithm (attenuation-weighted ordered subsets expectation maximization algorithm; 4 iterations, 8 subsets).

Low-dose CT protocol

After PET has been performed, the CT series is acquired immediately afterwards using a Siemens mCT Biograph 64. CT acquisition for PET involves low-dose CT (30 mAeff, 120 kV, 0.5 s/rotation, 5 mm layer thickness, pitch = 0.8). An effective dose of 1.7 mSv is to be expected for a low-dose CT of the thorax (scan length approx. 30 cm). The total additional radiation exposure of the PET/CT for the patient is 4 mSv (calculated with CT-EXPO v2.1).

Image evaluation

All CT and PET examinations are initially evaluated visually to determine the intensity and extent of the inflammatory processes. For semi-quantitative assessment of regional inflammatory activity, regions of interest (ROI) are placed in areas of increased [^{68}Ga]-pentixafor uptake using TrueD software (Siemens Medical Solutions, Knoxville, TN). The SUV(mean/max/peak) is calculated within the ROI according to the formula:

SUV = specific activity concentration (Bq/g) x body weight (in g) / injected activity (Bq). In addition to the SUV, other standard quantification parameters, such as the CXCR4-positive volume or mathematically extracted items (e.g., radiomics parameters, Interview Fusion, Mediso Medical Imaging, Hungary), are determined. In [68Ga]-pentixafor PET/CT, the SUVs are correlated with tracer uptake in the background (e.g., in the liver) and a ratio is formed.

6.5. Blood sampling

A venous cannula is inserted for the application of the tracer (see section 6.4). This cannula is used to collect 20 ml of EDTA blood and 5 ml of serum to determine the leukocyte profile, CXCL12, and CXCR4 antibodies (see section 4).

7. Adverse events and safety

